A randomized trial comparing perioperative pelvic **FLO**or physical therapy to current standard of care in transgender **Women** undergoing vaginoplasty for gend**ER** affirmation

The FLOWER Trial

[name] MPH; Staff, Center for Urogynecology & Pelvic Reconstructive Surgery; Subspecialty Care for Women's Health, Women's Health Institute, Cleveland Clinic, Cleveland OH

[name], CNP; Center for Urogynecology & Pelvic Reconstructive Surgery; Subspecialty Care for Women's Health, Women's Health Institute, Cleveland Clinic, Cleveland OH

BACKGROUND

In the natal male, the pelvic floor is comprised of bulbospongiosus, ischiocavernosus, deep transverse perineal, superficial transverse perineal, pubococcygeus, and obturator internus muscles; as well as the perineal body, external anal sphincter, anococcygeal ligament, coccyx, ischial tuberosities and the sacrotuberous ligament. Pelvic floor dysfunction, including urinary symptoms, bowel symptoms, sexual dysfunction and pelvic pain is often thought of a “female-centric” condition, and pelvic floor physical therapy (PFPT) is often used as first or second line therapy to treat many of these conditions in natal women. However, natal men also experience pelvic floor symptoms and while the literature is not as abundant in this patient population, there are data to support the use of physical therapy as primary and adjunctive therapy for many conditions in men.

In a prospective study by Masterson et al. (1) the authors evaluated 14 men with chronic pelvic pain syndrome who underwent a comprehensive PFPT program. Treatment included manual therapy (internal and external) of the pelvic floor and abdominal musculature to facilitate relaxation of muscles; therapeutic exercises to promote range of motion, improve mobility/flexibility and strengthen weak muscles; biofeedback to facilitate strengthening and relaxation of pelvic floor musculature; and neuromodulation for pelvic floor muscle relaxation and pain relief. A robust treatment response was found in 50% of patients while 20% reported a moderate response and 30% did not have a meaningful change. Longer duration of therapy predicted treatment response.

In a review of the literature by Cohen et al (2), the authors found that there was evidence supporting the association between the male pelvic floor and erectile dysfunction, ejaculatory/orgasmic dysfunction, and chronic prostatitis/chronic pelvic pain syndrome, respectively. The authors concluded that pelvic floor physical therapy is a necessary tool for the treatment of male

sexual dysfunction and pelvic pain. In a systematic review, PFPT was also been shown to be beneficial for the treatment of urinary incontinence in men who had undergone prostatectomy for prostate cancer (3).

Transgender women are individuals who were assigned male at birth (are biologically male), but identify as female. Vaginoplasty surgery is a gender-affirming genital surgery for transgender women seeking surgical transition. The goal of vaginoplasty is to create a natural-appearing vulva with a sensate clitoris, a female urethra, and in those patients who desire it, a vaginal canal. In constructing the neovaginal canal, a space is created between the rectum and the bladder, which requires dissection through the pelvic floor musculature. This dissection divides parts of the levator ani complex, which may affect pelvic floor function. As such, PFPT may have an important role in the perioperative management of transgender women undergoing vaginoplasty.

The only study published to date examining the effect of PFPT on all patients undergoing vaginoplasty was recently published by Jiang et al (4). In this retrospective analysis, the authors aimed to describe the incidence of pelvic floor dysfunction in transgender women undergoing gender-affirming vaginoplasty as well as to describe outcomes from their postoperative PFPT program. Over a two-year period, 77 patients were referred to PFPT postoperatively following vaginoplasty and all patients attended at least one session. Preoperatively, PFPT assessment identified an incidence of 42% for pelvic floor dysfunction and 37% for bowel dysfunction. Of those patients found to have dysfunction preoperatively, resolution after the first postoperative pelvic floor PT visit was 69% for pelvic floor dysfunction and 73% for bowel dysfunction. In addition, the authors found that the incidence of postoperative pelvic floor dysfunction was even lower in patients who attended pre- and postoperative PFPT versus postoperative PFPT alone.

There is further evidence that patients undergoing vaginoplasty surgery may have preoperative pelvic floor dysfunction symptoms that should be addressed before and after surgery. In a retrospective study by Manrique et al (5), patients scheduled to undergo male-to-female vaginoplasty were evaluated by a physical therapist for pelvic floor dysfunction and patients with pelvic floor symptoms underwent pre- and postoperative PFPT. The authors found that of the 40 patients evaluated, 31 (77.5%) were found to be symptomatic and that physical therapy significantly reduced severity of symptoms and its impact on daily living following surgery.

Currently, perioperative PFPT is not standard of care for all patients who undergo vaginoplasty surgery. While some practices have implemented these new programs, and the above data exist on outcomes associated with perioperative PFPT in transgender women undergoing vaginoplasty, no study has compared implementation of perioperative PFPT to routine care (no perioperative PFPT). Therefore, the primary objective of this study to compare the effectiveness of postoperative PFPT compared to no PFPT in transgender women undergoing vaginoplasty surgery for gender affirmation. Secondary objectives of the study are 1) to describe the incidence of preoperative pelvic floor dysfunction in transgender women undergoing PFPT and 2) to compare the

effectiveness of postoperative PFPT alone to pre- and postoperative PFPT in these patients.

STUDY METHODS

Study Design: Randomized double-blind study

Both subjects and the surgeon performing the surgery as well as the personnel administering questionnaires to patients postoperatively will be blind to randomization

Primary Aim

To compare the effectiveness of postoperative PFPT compared to no PFPT in transgender women undergoing vaginoplasty.

Primary Outcome: Patient reported ease of dilation at 12 weeks (VAS 0-10)

Secondary Outcome: Severity of pelvic floor dysfunction at 12 weeks (questionnaires)

Secondary Aims

To describe the incidence of preoperative pelvic floor dysfunction in transgender women undergoing PFPT.

To compare the effectiveness of postoperative PFPT alone to pre- and postoperative PFPT in these patients.

Primary Outcome: Patient reported ease of dilation at 12 weeks (VAS 0-10)

Secondary Outcome: Severity of pelvic floor dysfunction at 12 weeks (questionnaires)

Study Population: All transgender women undergoing vaginoplasty surgery through the Cleveland Clinic Transgender Surgery & Medicine Program at Cleveland Clinic Main Campus.

Inclusion Criteria:

- Age \geq 18 years of age
- Patients scheduled for full-depth vaginoplasty surgery

Exclusion Criteria:

- Inability to speak or comprehend the English language
- Patients scheduled for no-depth vaginoplasty surgery
- Patients who have undergone previous PFPT

- Patients who are s/p prostatectomy or treatment for prostate cancer

STUDY INTERVENTIONS

Recruitment, Enrollment and Randomization

Patients scheduled to undergo vaginoplasty surgery at Cleveland Clinic Main campus will be approached about voluntary participation in this study. This will occur over the phone approximately one to three months before their scheduled surgery. Patients who agree to participate will be sent a consent form via the mail and will be asked to sign consent in person. Enrollment and randomization will occur following informed consent. All patients will be given a copy of their signed and dated consent.

Once enrolled, patients will be randomized into one of two groups:

- Postoperative PFPT
- No Postoperative PFPT

If patients are randomized into the Postoperative PFPT arm, they will be further randomized into the following sub-arms:

- Postoperative PFPT alone
- Preoperative and Postoperative PFPT

Surgery

All patients will undergo vaginoplasty surgery by a single surgeon in a standard fashion. The neovaginal cavity will be created using the same technique across all patients. Postoperative care will be routine and the same for all patients.

Postoperative Pelvic Floor Physical Therapy

There will be three possible PFPT regimens. All PT regimens will be performed by the same two physical therapists, trained in the management of patients who have undergone vaginoplasty surgery.

- 1) No PFPT

Patients will present to see the physical therapist 3 weeks postoperatively. The following interventions will be performed:

Subjective assessment of bowel and bladder function. Visual and external palpation and assessment of external pelvic floor region. Intravaginal pelvic floor

assessment. Pelvic floor muscle dynamics and coordination assessment. Review of pelvic floor anatomy and function.

2) Postoperative PFPT Only

Patients will present to see the physical therapist 3 weeks and 6 weeks postoperatively. The following interventions will be performed:

3 weeks:

- Subjective assessment of bowel and bladder function
- Visual and external palpation and assessment of external pelvic floor region
- Intravaginal pelvic floor assessment
- Pelvic floor muscle dynamics and coordination assessment
- Instruction of pelvic floor coordination and lengthening
- Discussion of dilator program and progression
- Home program with instructions

6 weeks:

- External scar assessment and treatment if tissue healing allows
- Instruction to patient of scar mobilizations
- Intravaginal pelvic floor assessment and treatment if indicated
- Review of pelvic floor lengthening and coordination
- Review and progression of dilator program if appropriate
- Assessment of current bowel/bladder symptoms; home program and instructions to address these symptoms

3) Preoperative PFPT and Postoperative PFPT

Patients will present to see the physical therapist 3 weeks before surgery, 3 weeks and 6 weeks postoperatively. The following interventions will be performed:

Preoperative:

- Diaphragmatic breathing
- Discuss dilator positioning/introduce dilator program
- External pelvic floor assessment
- Teach pelvic floor coordination
- Assessment of current bowel/bladder symptoms; home program and instructions to address these symptoms

3 weeks:

- Subjective assessment of bowel and bladder function
- Visual and external palpation and assessment of external pelvic floor region
- Intravaginal pelvic floor assessment
- Pelvic floor muscle dynamics and coordination assessment
- Instruction of pelvic floor coordination and lengthening
- Discussion of dilator program and progression
- Home program with instructions

6 weeks:

- External scar assessment and treatment if tissue healing allows
- Instruction to patient of scar mobilizations
- Intravaginal pelvic floor assessment and treatment if indicated
- Review of pelvic floor lengthening and coordination
- Review and progression of dilator program if appropriate
- Assessment of current bowel/bladder symptoms; home program and instructions to address these symptoms

Study Questionnaires & Exams

All patients will be administered questionnaires preoperatively and 12 weeks postoperatively. The following questionnaires will be administered:

Preoperatively:

- CRAD-8 and UDI-6
- PFIQ-7

Postoperatively 1 week (at the time of routine dilation teaching):

- Vaginal length (routine exam)

Postoperatively 12 weeks:

- CRAD-8 and UDI-6
- PFIQ-7
- PGI-I
- Ease of Passing Dilator (VAS 0-10)
- Pain with Dilation (VAS 0-10)
- Largest dilator size used
- Vaginal length (routine exam)

Cross-Over Treatment

Any patients in the No PFPT arm who are determined to have pelvic floor dysfunction or symptoms that may benefit from PFPT referral, will be referred after the 12-week mark. Any patient in one of the PFPT arms who is determined to still need PFPT for persistent pelvic floor dysfunction or symptoms will be referred for continued care.

DATA COLLECTION & MANAGEMENT

Data Collection:

In addition to the above-mentioned questionnaires and exam findings, the following data will be collected from the electronic medical record before surgery and 12 weeks postoperatively:

- MRN
- Age
- BMI
- Length of preoperative hormone therapy
- Previous orchiectomy
- Comorbid medical conditions: cardiac, pulmonary, diabetes, autoimmune
- Chronic pain: lower back pain, fibromyalgia, arthritis, other
- Intraoperative complications: bleeding, visceral injury, other
- Postoperative complications: wound issues, hematoma/seroma, infection, anatomic urinary stream issues, fistula, other
- PFPT utilization beyond 6 and 12 weeks postoperatively

Data Management:

Protection of each subject's personal health information will be a priority in this study. One master excel file containing subject personal information including name and medical record number will be kept in a password-protected file, on a designated protected research drive on a password-protected computer in a locked office at the Cleveland Clinic. In that file, each subject will be assigned a subject identification number that will be used for the purposes of data collection in order to de-identify subjects.

All paper forms used for data collection will be kept in a research cabinet dedicated to this project which will be locked at all times, in a locked office at the Cleveland Clinic. All forms will contain de-identified information – identification numbers will correspond to the subjects listed in the master excel file.

[figure not shown]
All study data will be transferred and managed electronically using REDCap (Research Electronic Data Capture). Each subject will be entered into REDCap using the assigned identification number from the master excel file. REDCap is a secure, web-based application designed to support data capture for research studies, providing user-friendly web-based case report forms, real-time data entry validation, audit trials, and a

de-identified data export mechanism to common statistical packages. The system was developed by a multi-institutional consortium which was initiated at Vanderbilt University and includes the Cleveland Clinic. The database is hosted at the Cleveland Clinic Research Datacenter in the JCN basement and is managed by the Quantitative Health Sciences Department. The system is protected by a login and Secure Sockets Layers (SSL) encryption. Data collection is customized for each study as based on a study-specific data dictionary defined by the research team with guidance from the REDCap administrator in Quantitative Health Sciences at the Cleveland Clinic.

POWER ANALYSIS & STATISTICS

There will be 2 arms to this study: No Postoperative PFPT and Postoperative PFPT. The Postoperative PFPT arm will be further randomized into two other arms: Postoperative PFPT Only and Preoperative and Postoperative PFPT.

The primary aim is to compare the effectiveness of postoperative PFPT compared to no PFPT in transgender women undergoing vaginoplasty using Ease of Dilation (VAS 0-10) as the primary outcome. We determined that 17 subjects in each arm were needed to detect a difference of 2 (+/-1) points between the two groups (No Postoperative PFPT vs Postoperative PFPT) with 80% power and a significance level of 0.05. We will account for potential subject drop out and loss to follow-up as well as unforeseen factors in recruiting and will plan to recruit 20 subjects to each arm, for a total of 40 subjects.

Continuous descriptive data will be reported as mean and standard deviation (\pm SD) or median with interquartile range (IQR), depending on distribution. Categorical data will be reported as frequencies, using percentages. Ease of dilation and pelvic floor symptoms will be compared between arms (No PFPT vs Postoperative PFPT). The investigators also plan to perform a subgroup analyses, comparing patients who

underwent postoperative PFPT only to those who underwent both preoperative and postoperative PFPT.

Ease of dilation (mean) and pelvic floor symptoms (mean difference from baseline) will be compared as a continuous variables using a student' t test to compare between the two groups. Binary logistic regression will be used to assess the influence of various patient factors on the patient reported ease of dilation as well as pelvic floor symptoms and results will be reported as odds ratios with 95% confidence intervals.

JMP 14.0 (SAS Institute Inc., Cary, NC) will be used for all statistical analyses. The primary investigator ([name]) will perform the statistical analysis. All results yielding $p < 0.05$ will be deemed statistically significant.

All analyses will be conducted using an intention-to-treat principle. The investigators anticipate that some non-adherence to the assigned intervention (e.g. crossover to the postoperative PFPT arm) may occur if patients are determined to be symptomatic requiring PFPT per the surgeon's discretion, and as these protocol deviations will bias the results towards superiority of the intervention, a per-protocol sensitivity analysis has also been planned.

REFERENCES

- 4) Jiang DD¹, Gallagher S, Burchill L, Berli J, Dugi D. Implementation of a Pelvic Floor Physical Therapy Program for Transgender Women Undergoing Gender-Affirming Vaginoplasty. *Obstet Gynecol* 2019; 133(5):1003-1011.

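### The protocol calls the trial double-blind with subjects blind, but the regimens differ in visits and content and no masking method is given for a self-rated primary outcome

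*Combined protocol and SAP*

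**What the plan says.** In the combined protocol and SAP, Study Methods gives the design as "Randomized double-blind study" and adds: "Both subjects and the surgeon performing the surgery as well as the personnel administering questionnaires to patients postoperatively will be blind to randomization". The primary outcome is "Patient reported ease of dilation at 12 weeks (VAS 0-10". The secondary outcome is questionnaire severity of pelvic floor dysfunction at the same time point.

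The section on Postoperative Pelvic Floor Physical Therapy sets out three regimens:

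- No PFPT: "Patients will present to see the physical therapist 3 weeks postoperatively". The visit consists of four assessments and a review of anatomy.
- Postoperative PFPT Only: "Patients will present to see the physical therapist 3 weeks and 6 weeks postoperatively". The 3-week list includes "Home program with instructions", along with coordination and lengthening instruction and a dilator-program discussion.
- Preoperative and Postoperative PFPT: the same two visits, plus one 3 weeks before surgery.

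Some features help masking. On the therapists, the plan says "All PT regimens will be performed by the same two physical therapists". The exclusion criteria include "Patients who have undergone previous PFPT", so subjects should have no earlier course of therapy to compare with. Postoperative care is otherwise the same for everyone, and dilation teaching at 1 week is described as routine.

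**The concern.** A claim that subjects are blind needs regimens that feel alike to the subject, or an account of how she is kept from recognising hers. The protocol gives neither for the parts of the regimens that differ.

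This matters because of who rates the outcome. The ease-of-dilation VAS, the pain VAS, the symptom questionnaires and the PGI-I all come from the subject. Masked staff can avoid prompting her, but they do not make the rating itself blind. If subjects know or guess their arm, a between-arm difference can contain an expectation effect as well as an effect of the therapy. A report that follows the protocol's wording would tell readers that this had been excluded by design.

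The planned per-protocol analysis does not help. It is there for crossover and does nothing about expectation.

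**Working it through.** No sample-size or power arithmetic bears on this point. The check sets the blinding statement beside the regimens as written.

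**Step 1. What each subject experiences** (from the regimen lists and Study Questionnaires & Exams):

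| Time | No PFPT | Postoperative PFPT Only | Preoperative and Postoperative PFPT |
|---|---|---|---|
| 3 weeks before surgery | no therapist visit | no therapist visit | visit: breathing, introduction to dilator program, external assessment, coordination teaching, bowel/bladder assessment with home program |
| 1 week after | routine dilation teaching | same | same |
| 3 weeks after | visit: four assessments, anatomy review | visit: same four assessments, plus coordination and lengthening instruction, dilator-program discussion, home program | as Postoperative PFPT Only |
| 6 weeks after | no therapist visit | visit: scar work, intravaginal assessment and treatment if indicated, review of lengthening and coordination, dilator-program progression, bowel/bladder home program | as Postoperative PFPT Only |
| Therapist visits | 1 | 1 + 1 = 2 | 1 + 1 + 1 = 3 |

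**Step 2. What is matched.** The 3-week visit is matched in timing, therapists and its four assessments. A few assessments at the 6-week and preoperative visits resemble ones that control subjects have at 3 weeks (intravaginal, external, bowel and bladder), but the visits themselves have no counterpart.

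**Step 3. What is not matched.** The 6-week visit, the preoperative visit, the dilator-program discussion and progression with the therapist, and the home programs have no equivalent under No PFPT. The dilator work lies close to what the primary VAS asks about. In the secondary comparison of the two PFPT sub-arms, the listed difference is the preoperative visit itself, and nothing stands in for it.

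**Step 4. Is a masking method given?** The protocol text does not call the control visit a sham or say that it serves blinding. It does not say what subjects are told about the other schedules, or how they are kept unaware of their arm.

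**Step 5. Who assesses the outcome?** The subject does, for the primary VAS and all the questionnaires. The blinding that could be achieved for questionnaire personnel does not reach the rating.

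**The case against.** The strongest reply is that a subject sees only her own regimen. Different schedules unmask her only if she knows what the others receive. A subject with no previous PFPT who has a hands-on external and intravaginal assessment and an anatomy review from a trained therapist could believe that she received the therapy. The protocol itself lists that visit among its PFPT regimens. What subjects are told would normally be in the consent form, which was not available, so its content cannot be counted as missing.

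This stands as a limit on the conclusion. A reader might infer from the visit counts that subject blinding is impossible, or that subjects will in fact be unmasked. The documents do not establish either. What remains is that the protocol asserts blinding, prescribes regimens that differ openly, and leaves the reader no way to see how the two fit together.

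A second reply is that the question is effectiveness against routine care, where expectation may be part of the effect. That is a fair position, and the randomised comparison stays valid for that question. It argues for dropping the label, not for keeping it.

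**Conclusion.** The point holds: the statement that subjects are blind, and the double-blind label that depends on it, are wrong as written. The regimens involve 1, 2 or 3 therapist visits with different content, the control visit covers only part of the difference, and the protocol text describes no masking. The conclusion rests on that text alone. Consent material that explains the masking could change it.

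The documents give no estimate of an expectation effect on the VAS, so no size is put on it. Two stronger readings should be resisted:

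- **That the primary result will be biased by some stated amount, or is invalid.** Nothing in the documents supplies the size of such a bias or shows that it will occur. The consequence is for labelling and interpretation.
- **That the surgeon is also shown to be unblinded.** Under Cross-Over Treatment, No PFPT subjects are referred only after the 12-week mark, so that rule does not reveal allocation before the endpoint. The surgeon-discretion crossover anticipated in Power Analysis & Statistics is a separate matter, to be reconciled with surgeon blinding on its own terms.

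**What to change.** Reconcile the Study Design statement with the regimen descriptions. If subjects are to be kept unaware of their arm, state how. Otherwise:

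1. Delete the term double-blind and the claim that subjects are blind.
2. Limit the blinding statement to roles that can be masked, such as the questionnaire personnel.
3. Add to the statistics section: *Between-arm differences in the VAS and questionnaires include any expectation effect and will not be reported as double-blind results.*

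The second route changes wording only and leaves the regimens, sample size and primary analysis as they are. Its cost is the loss of the double-blind label. The first route needs a masking description that agrees with what the consent form tells subjects about the other schedules, so it may reach the consent wording too.

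### Pelvic floor symptom scores are compared by t test on change from baseline; adjusting the 12-week score for baseline would generally be more precise at almost no cost

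*Combined protocol and SAP*

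**What the plan says.** Under both comparative aims (Study Methods) the plan lists "Secondary Outcome: Severity of pelvic floor dysfunction at 12 weeks (questionnaires"). Study Questionnaires & Exams states: "All patients will be administered questionnaires preoperatively and 12 weeks postoperatively". CRAD-8, UDI-6 and PFIQ-7 appear on both the preoperative and the 12-week list, so each patient should have a baseline and an outcome score. Ease of passing the dilator appears only at 12 weeks.

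The analysis is set out in Power Analysis & Statistics: "Ease of dilation (mean) and pelvic floor symptoms (mean difference from baseline) will be compared as a continuous variables". The test named for both outcomes is Student's two-sample t test. The main contrast is no PFPT against postoperative PFPT, with both therapy sub-arms pooled. A second comparison is introduced with "The investigators also plan to perform a subgroup analyses, comparing patients who" had postoperative therapy only with those who had it before and after surgery. On numbers, the plan needs 17 per main arm and "will plan to recruit 20 subjects to each arm, for a total of 40 subjects".

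The only regression mentioned is this: "Binary logistic regression will be used to assess the influence of various patient factors". It addresses patient factors and is not a baseline-adjusted comparison of the arms. No such comparison appears anywhere in the document.

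**The concern.** Subtracting baseline assumes that a patient one point worse before surgery will, on average, be one point worse at 12 weeks. If the true slope is below 1, as it is whenever the SDs are equal and the correlation is less than perfect, the change score over-corrects and carries baseline noise into the comparison. ANCOVA estimates the slope from the data.

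Symptom severity is the secondary outcome of both comparative aims. The trial has 17-20 patients per main arm, and 17-20 in total for the sub-arm comparison. At that size, avoidable variance matters, and a single-surgeon programme cannot easily recover it by recruiting more patients.

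**Working it through.** **Inputs from the documents.** N = 34 evaluable (17 per arm) or 40 enrolled for the main contrast; N = 17 or 20 in total for the sub-arm contrast. The plan gives no power or precision figure for the questionnaires, so there is none to reproduce. Its 17 per arm was derived for ease of dilation and serves here only as a patient count.

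**Assumptions, not in the documents.** Correlation rho between baseline and 12 weeks of 0.3, 0.5 or 0.7; ratio k of the 12-week SD to the baseline SD; sub-arm split near 1:1; roughly normal baseline scores.

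**Formulas** (baseline SD set to 1, per-patient variance):

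- Change score: 1 + k² − 2·rho·k
- ANCOVA: k²(1 − rho²) × [1 + 1/(N − 4)], where the bracket is the cost of estimating the slope
- Before that cost, change minus ANCOVA = (1 − rho·k)², which is never negative

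ANCOVA can therefore lose only near a true slope rho·k of 1, and by at most 1/(N − 4): 1/30 = 3.3% at N = 34, 1/36 = 2.8% at N = 40, 1/16 = 6.3% at N = 20 and 1/13 = 7.7% at N = 17.

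**Example, N = 34, k = 1, rho = 0.5.** Change: 1 + 1 − 1 = 1. ANCOVA: 0.75 × 1.0333 = 0.775. Reduction: 22.5%.

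**Variance reduction from ANCOVA (%); negative values are losses**

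| Contrast | k | rho 0.3 | rho 0.5 | rho 0.7 |
|---|---|---|---|---|
| Main, N = 34 | 0.75 | 52.5 | 46.3 | 42.2 |
| | 1 | 32.8 | 22.5 | 12.2 |
| | 1.25 | 18.9 | 7.7 | −1.3 |
| | 1.5 | 10.0 | 0.4 | −3.1 |
| Sub-arm, N = 20 | 1 | 30.9 | 20.3 | 9.7 |
| | 1.25 | 16.6 | 5.1 | −4.2 |
| | 1.5 | 7.4 | −2.5 | −6.0 |
| Sub-arm, N = 17 | 1 | 30.0 | 19.2 | 8.5 |
| | 1.25 | 15.5 | 3.8 | −5.6 |
| | 1.5 | 6.2 | −3.8 | −7.5 |

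At N = 40 with k = 1 the main-contrast gains are 33%, 23% and 13%.

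**Where ANCOVA loses, N = 34.** With k = 1, only if rho exceeds 2/1.0333 − 1, about 0.94. With k = 1.25, for rho 0.66-0.88. With k = 1.5, for rho 0.51-0.78.

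**What the gain is worth, N = 34, k = 1.** The 95% CI narrows by 1 − √0.672 = 18%, 1 − √0.775 = 12% and 1 − √0.878 = 6%. A change-score test would need 17/0.672 = 25.3, 17/0.775 = 21.9 and 17/0.878 = 19.4 patients per arm to match.

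**Simulation** (100,000 trials per setting, 17 against 17, k = 1) gave the same variance gains. Power at rho 0.3, 0.5 and 0.7, for assumed differences in 12-week SD units:

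| Difference | Change score | ANCOVA |
|---|---|---|
| 0.5 SD | 22.4 / 29.4 / 44.9% | 30.8 / 36.3 / 49.8% |
| 0.8 SD | 48.1 / 61.8 / 83.1% | 64.2 / 72.8 / 87.5% |

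Type I error was 4.9-5.1% for both tests with normal scores. With scores floored so that half were zero, it was 4.7-5.0% for both at 17 against 17, and 4.5-4.7% (change) and 4.4% (ANCOVA) at 8 against 9.

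**The case against.** **The planned test is not wrong.** This stands. The choice is between two valid analyses of a secondary outcome, and no figure in the plan is contradicted. Nor does ANCOVA rescue the outcome: at a 0.5 SD difference both tests remain underpowered.

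**The 12-33% gain rests on equal SDs.** This also stands. The Background says of the surgery: "This dissection divides parts of the levator ani complex, which may affect pelvic floor function". That makes a larger spread of scores at 12 weeks plausible, and in the table the main-contrast gain is then nil or negative in three of six cells. But those losses are at most 3.1%, against gains of up to 18.9% in the same rows. The trade still favours ANCOVA for the main contrast. For the sub-arm contrast it is weaker.

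**Baseline may not precede treatment.** The questionnaires are described only as preoperative, while one sub-arm has a therapy visit 3 weeks before surgery. If baseline were recorded after that visit and scores had shifted, neither method would estimate the 12-week effect. With a baseline shift D0 and a 12-week effect D1, change estimates D1 − D0 and ANCOVA estimates D1 − b·D0, where b is the slope. Taking D1 = −0.50 and D0 = −0.19 as an assumed illustration, change gives −0.31, and ANCOVA gives −0.44 at b = 0.3 and −0.37 at b = 0.7. ANCOVA is closer to the truth for any slope between 0 and 1. The timing should be fixed under either method; it is no reason to keep the change score.

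**Conclusion.** The concern holds, as an improvement in precision and not as an error. For the main contrast, ANCOVA offers a potential variance reduction of about a third against a loss capped at about 3%. The exact gain cannot be fixed, because it depends on the unreported correlation and SD ratio, and it may be nil. For postoperative-only against pre- and postoperative therapy the case is optional, since the loss can reach 6.3% at 20 patients and 7.7% at 17. The statement that both methods estimate the same arm difference assumes a baseline recorded before any study therapy. Ease of dilation has no baseline score, so its analysis and the sample size stand apart from this point.

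**What to change.** In Power Analysis & Statistics, replace the t test on change for the arm comparison of pelvic floor symptoms with wording such as:

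> Each 12-week CRAD-8, UDI-6 and PFIQ-7 score will be compared between randomised arms in a linear model with arm and that questionnaire's baseline score as covariate. The adjusted mean difference will be reported with its 95% CI. Baseline is the score recorded before any preoperative PFPT visit.

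The same model may be used for the sub-arm comparison if the SAP acknowledges the larger cost of estimating the slope there. The change should be made before the data are analysed.

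The cost is the SAP wording and one residual degree of freedom per model: 31 instead of 32 at N = 34, and 14 instead of 15 at N = 17. No new questionnaire or visit is needed, and standard software fits the model.
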